5.6 Noncompliance

All instances of protocol deviations will be recorded according to the study specific monitoring plan.

6.0 TREATMENT OF SUBJECTS

6.1 Drug Preparation and Administration

Both HS-130 and HS-110 drug products will be administered via intradermal injections/re-injections based on the dose levels as defined in the dose escalation scheme (Section 6.1.1) on Day 1 of each cycle.

If any serious adverse reaction occurs these may be treated per institutional practice, as noted in Section 6.4 Concomitant Medication.

The HS-130 final drug product is packaged in single-dose vials as fully-diluted frozen liquid filled under aseptic conditions in 1.2 mL cryovials, containing 0.6 mL suspension of 2×10^7 cells/mL (targeted) in a cryopreservative buffer, with a final formulation of 0.567% sodium chloride, 0.5% human serum albumin (HSA), 0.007% sodium bicarbonate, 6% pentastarch, and 5% dimethyl sulfoxide (DMSO).

HS-110 (viagenpumatulcel-L) is packaged in single-dose vials as fully-diluted frozen liquid filled under aseptic conditions in 1.2 mL cryovials, containing 0.6 mL suspension of 2×10^7 cell/mL (targeted) in a cryopreservative buffer, with a final formulation of 0.567% sodium chloride, 0.5% HSA, 0.007% sodium bicarbonate, 6% pentastarch, and 5% DMSO.

Each patient will be administered up to a total of 10 spatially divided intradermal injections/re-injections of ≤ 0.14 mL per injection, depending on the required HS-130 and HS-110 dose levels. HS-130 will be injected first, and a period of no less than 2 minutes, but no more than 5 minutes, should elapse before administering HS-110. HS-110 must be injected into the same exact location as the HS-130 injections (re-injected sites). There are some dose levels (3, 5, 6, and 7) where the number of HS-110 injections will exceed the number of HS-130 injections. In these cases, after all HS-130 sites have been re-injected, the HS-110 may be administered in a new spatially divided injection site.

At each cycle, the injection region will alternate between the left shoulder and right shoulder. The HS-130 and HS-110 injections will all be administered into the designated injection region for that cycle (left shoulder or right shoulder) to increase volume distribution and enhance antigen presentation to lymph node regions.

Table 1: HS-130/HS-110 Dose Administration Guidelines

Dose Level	Study Drug	Total mL	Volume (mL) per Injection							
			Injection #1	Injection #2	Injection #3	Injection #4	Injection #5	Injection #6	Injection #7	
-1	HS-130	0.02	0.02							
	HS-110	0.06	0.06							
1	HS-130	0.04	0.04							
	HS-110	0.10	0.10							
2	HS-130	0.10	0.10							
	HS-110	0.10	0.10							
3	HS-130	0.10	0.10							
	HS-110	0.22	0.12	0.10						
4	HS-130	0.18	0.10	0.08						
	HS-110	0.22	0.12	0.10						
5	HS-130	0.18	0.10	0.08						
	HS-110	0.44	0.12	0.12	0.10	0.10				
6	HS-130	0.36	0.12	0.12	0.12					
	HS-110	0.44	0.12	0.12	0.10	0.10				
7	HS-130	0.36	0.12	0.12	0.12					
	HS-110	0.86	0.14	0.12	0.12	0.12	0.12	0.12	0.12	0.12

Drug products will be supplied to clinical sites via shipments in liquid nitrogen dry-shipper units, which will be validated to maintain cryogenic temperatures for up to 10 days. Upon arrival, the products will be transferred to controlled liquid nitrogen storage at the clinical site in the liquid nitrogen vapor phase until ready for preparation. Study staff must take care to minimize temperature excursions during transfer of the product from shipping containers to controlled liquid nitrogen storage on site.

Drug products will not be retrieved from cryogenic storage until the study subject is present and available for dosing. When removing a product carton from storage to retrieve a vial for dosing, any doses remaining in the carton will be returned to cryogenic storage immediately. Study drugs must be administered within 2 hours of retrieval from the dewar (cryogenic storage).

Stability studies for HS-130 are currently ongoing and clinical sites will be notified of storage information and/or shelf life change. The instructions for preparation, administration, stability and storage of HS-110 to be used in combination with HS-130 will reference instructions per the Investigational Product Manual.

6.1.1 Dose Escalation Scheme

Escalating doses of the viable, replication-incompetent, human whole cell vaccines, HS-130 and HS-110 will be administered to patients via intradermal injections/re-injections (up to 10 total) on Day 1 of a two-

week cycle. The length of each cycle is two weeks, and the DLT window of observation includes the safety data obtained from the first two treatment cycles, Cycle 1 and Cycle 2 (4 weeks).

Seven dose levels will be explored, and patients will receive separate escalating doses of HS-130 and HS-110 in alternating fixed 1:1 or 2:1 ratio based on the amount of secreted OX40L-Ig (HS-130) and gp96-Ig fusion protein (HS-110) per cell of the drug product. The starting dose of HS-130/HS-110 combination is based on the dose-ranging studies conducted in animal models of T cell expansion and tumor challenge, as well as established clinical experience from HS-110.

Table 2: HS-130/HS-110 Dose Levels

Cohort	Dose level	HS-130 dose* (ng/24-hr OX40L-Ig)	HS-110 dose* (ng/24-hr gp96-Ig)	HS-130: HS-110 Ratio	Total number of AD100 cells (Q2W) [#]	Minimum number of patients
1	-1	75 ng/24-hr	75 ng/24-hr	1:1	1.0 million	1
	1	150 ng/24-hr	150 ng/24-hr	1:1	1.9 million	1
	2	300 ng/24-hr	150 ng/24-hr	2:1	2.3 million	1
	3	300 ng/24-hr	300 ng/24-hr	1:1	3.8 million	1
	4	600 ng/24-hr	300 ng/24-hr	2:1	4.7 million	1
2	5	600 ng/24-hr	600 ng/24-hr	1:1	7.6 million	3
3	6	1,200 ng/24-hr	600 ng/24-hr	2:1	9.3 million	3
4	7	1,200 ng/24-hr	1,200 ng/24-hr	1:1	15.1 million	3

*The number of cells administered to achieve the HS-130 (ng/24-hr of OX40L-Ig protein) and HS-110 (ng/24-hr of gp96-Ig protein) dose will be determined based on the specifications for that batch of the drug product. For HS-130: Lot HBI-HS-130-FP-001 = 241 fg/cell/24-hr and HS-110: Lot 0000748931 = 104 fg/cell/24-hr. The productivity per cell will be determined using the same assay format and standards for pre-clinical and clinical derived material.

[#] The suggested total number of allogeneic tumor cells (AD100) administered every second week at the highest dose level is similar to or less than the weekly dose of 10 million HS-110 cells that has been established safe and immunologically effective in the HS-110 study (NCT02439450, IND No. 14814).

The first cohort will employ an accelerated design to evaluate the first 4 dose levels in single patients. There will be a staggered enrollment with a minimum 1-week delay between each patient in cohort 1. If any drug-related \geq Grade 2 (other than Grade 2 injection site reaction with pain) event occurs during the first cycle of treatment, the study will revert to 3+3 design starting at that dose level.

Subsequent cohorts in the dose escalation phase will enroll patients following the standard 3+3 design. Three patients will be enrolled in each subsequent dose cohort and enrolled with a (minimum) 1-week staggered delay (i.e. Patient 2 to be dosed \geq 1-week after Patient 1 received the first dose, and Patient 3 to be dosed \geq 1-week after Patient 2 received the first dose).

In the 3-patient cohorts (i.e. 3 patients treated at the same dose), if 1 out of 3 patients experience a DLT during the first two treatment cycles, the dose cohort will be expanded up to 6 patients. If \geq 2 out of 6 patients experience DLTs, the MTD has been exceeded, and dose escalation will cease. Up to 3 additional patients will be enrolled at the next lowest dose if only 3 patients were treated at that dose level, to confirm safety of that dose. If a DLT is observed already with the first patient in Cohort 1, the Safety Review

Committee (Section 8.1.2.8.1) may suggest and approve a dose de-escalation cohort with at least 50 % reduction of HS-110 and HS-130 (dose level -1).

Once all patients in a cohort have completed the first two cycles of dosing and received at least 2 doses of HS-130/HS-110, the safety and tolerability of the combination treatment administered will be reviewed by the safety review committee (SRC). If 0 out of 3 patients or 1 out of 6 patients experience a DLT, then the SRC may recommend enrollment at the next higher dose level.

Any patient who does not receive two doses of the study treatment during the DLT window of observation (first 2 cycles/4 weeks), for reasons other than study drug-related toxicity and did not experience a DLT will not be taken into account in the assessment of the overall DLT rate for the particular dose level cohort and will be replaced.

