9. Any ongoing anticancer therapy including; small molecules, immunotherapy, chemotherapy, monoclonal antibodies, radiation (curative/treatment intent) or any other experimental drug. Prior therapy must be stopped within four weeks before first infusion in the study, or 5 half-lives, or twice the duration of the biological effect of the investigational product (whichever is shortest). Adjuvant anti-hormonal treatment(s) for previously treated breast cancer or prostate cancer are allowed. Bisphosphonates are allowed, Denosumab and other RANK ligand inhibitors are prohibited. Note that palliative radiation only requires a two week washout.
10. Known current malignancy other than inclusion diagnosis. Prior curable cancer with complete remission for >2 years is allowed.
11. Any other ongoing significant, uncontrolled medical condition as per Investigator discretion.
12. Received a live vaccine within 30 days prior to first dose of study drug.
13. Clinically significant active viral, bacterial or fungal infection requiring:
 - a. Intravenous treatment with antimicrobial therapy completed less than two weeks prior to first dose, or
 - b. Oral treatment with antimicrobial therapy completed less than one week prior to first dose.Prophylactic treatment with antibiotics (e.g. for dental extractions) is allowed.
14. Known positive serology for human immunodeficiency virus (HIV), hepatitis B, or hepatitis C (except in cases of immunity after cured infection). Testing not required.

15. Substance abuse, medical, psychological or social conditions that may interfere with the patient's participation in the trial or evaluation of the trial result in the opinion of the Investigator.
16. Women who are pregnant or breast feeding.

Test product, dose and mode of administration:

Each patient will be administered separate intradermal injections (at the same injection sites) of HS-130 (Lot HBI-HS-130-FP-001: OX40L-Ig concentration = 338 ng OX40L-Ig/10⁶ cells/24-hr) and HS-110 (Lot 0000748931: gp96-Ig concentration = 104 ng gp96-Ig/10⁶ cells/24-hr) based on the dose levels as defined in the dose escalation scheme (Section 6.1.1) on Day 1 of each cycle.

Dose-limiting toxicity (DLT):

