Heat Biologics future development plan is to produce a combination therapy incorporating both T cell costimulation (OX40L-Ig) and vaccination (gp96-Ig) in one commercialized product using a single vector in a single cell line (AD100). After determining the optimal dose range of co-administered HS-110 and HS-130 from this clinical study, the combination will continue to be developed and evaluated in additional clinical trials of safety and efficacy after selection, manufacturing and clinical development of the combined product on a single vector/single cell line. The quantity of gp96-Ig and OX40L-Ig fusion proteins secreted by the combined product would be designed to mimic the same optimal dose level determined to be immunologically active from the initial studies conducted with HS-110 and HS-130. Heat Biologics understands that this development change constitutes a new drug product and will require a new IND

submission.

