To establish the acute effects in terms of cytokine and chemokine release, a non-GLP study¹⁶ was conducted in mice to establish the differences between xenogeneic (HS-130) vs. same species (mHS-130) vs. a mouse OX40 agonist antibody. Five single escalating doses of HS-130, mHS-130, and an agonist OX40 antibody were administered to mice to determine a cell number threshold of HS-130, that can induce a robust xenogeneic rejection response in mice, as measured by systemic cytokine release. Significant responses were seen for the cytokines: IL-17A, ICL10, MCP-3/CCL7, MIP-1-beta/CCL4, TNF-alpha, Gro-alpha/KC/CXCL1, which could be partially attributed to an anti-human, xenotransplantation response and/or related to the expected innate immune response to foreign cellular matter, required to remove foreign protein particles. Significant response was only observed for the highest cellular dose tested. The No Observed Adverse Effect Level (NOAEL) was determined to be 400 µg (20 mg/kg) for agonist OX40 antibody, 219.5 ng/24-hr per animal (0.0109 mg/kg) and 387.2 ng/24-hr per animal (0.0193 mg/kg) for HS-130 and mHS-130, respectively.

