- Represents less than 1/10th of the safe and effective current clinical dose for HS-110 (IND 14814). At the highest suggested dose in this study, HS-110 is given at approximately 0.8 of the documented HS-110 dose currently administered in patients.

- More than 2.5-fold below the absolute dose (ng per injection) NOAEL (no significant cytokine/chemokine release) of mHS-130 alone in mice.

To escalate the dose level, we propose the next dose at a 2:1 ratio of HS-130 to HS-110 (300 ng/24-hr OX40L-Ig to 150 ng/24-hr gp96-Ig) and so forth as described in the dose escalation scheme (Section 6.1.1). This approach is designed to bracket the HS-130 to HS-110 dose ratio findings in the mouse study.

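### HS-130 lot HBI-HS-130-FP-001 has two potencies, 338 in the Synopsis and 241 fg/cell/24-hr in the Table 2 footnote; the Table 2 cell totals for levels 1 to 7 agree with 338, not with the footnote

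*Combined protocol and SAP*

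**What the plan says.** The Synopsis, under the test product entry, reads "Lot HBI-HS-130-FP-001: OX40L-Ig concentration = 338 ng" per million cells per 24 hours. The footnote to Table 2 in Section 6.1.1 reads "For HS-130: Lot HBI-HS-130-FP-001 = 241 fg/cell/24-hr and HS-110: Lot 0000748931 = 104 fg/cell/24-hr". The HS-110 lot is 104 in both places.

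The same footnote says that the number of cells given to reach each ng "dose will be determined based on the specifications for that batch of the drug product". Table 2 prints total AD100 cells of 1.0, 1.9, 2.3, 3.8, 4.7, 7.6, 9.3 and 15.1 million for levels -1 and 1 to 7. A second footnote compares "The suggested total number of allogeneic tumor cells (AD100) administered every second week at the highest dose level" with earlier HS-110 dosing.

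Table 1 in Section 6.1 prints fixed injection volumes. The only concentration given there is 2 x 10^7 "cells/mL (targeted) in a cryopreservative buffer", for both products.

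Section 2.5 supports the 150 ng starting dose partly as "More than 2.5-fold below the absolute dose (ng per injection) NOAEL" of the mouse surrogate. Section 2.3.2 gives that NOAEL as "387.2 ng/24-hr per animal (0.0193 mg/kg) for HS-130 and mHS-130, respectively".

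**The concern.** Potency is the conversion factor between the dose label and what goes into the syringe. Two values for one lot, both in current text and in equivalent units, mean that someone working from Section 6.1.1 and someone working from the Synopsis would calculate different HS-130 cell numbers for the same labelled dose. The protocol does not say which value prevails, and the total-cell column of Table 2 disagrees with its own footnote at levels 1 to 7.

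The ng label supports the starting-dose margin and the intended 1:1 and 2:1 ratios. It also informs later work: of a future single-cell product, Section 2.1 says "The quantity of gp96-Ig and OX40L-Ig fusion proteins secreted by the combined product would be designed to mimic the same optimal dose level" found here. That would be a new drug product under a new IND with its own trials, so a wrong label would not pass forward unchecked, but it would be the design target.

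**Working it through.** **Inputs.** HS-130 potency 338 (Synopsis) or 241 (Table 2 footnote); HS-110 potency 104 (both); ng doses and printed totals from Table 2; volumes from Table 1; target concentration 20 million cells/mL (Section 6.1); mouse surrogate NOAEL 387.2 ng (Section 2.3.2).

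**Units.** 1 ng = 10^6 fg, so 338 ng per 10^6 cells is 338 fg/cell. The conflict is 338/241 = 1.40.

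**Step 1: reproduce Table 2.** Total cells (million) = HS-130 ng / HS-130 potency + HS-110 ng / 104. For level 7 at 338: 1,200/338 + 1,200/104 = 3.55 + 11.54 = 15.09. At 241: 4.98 + 11.54 = 16.52. The last column solves for HS-130 potency from the printed total, allowing 0.05 million either way for rounding.

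| Level | ng HS-130 / HS-110 | Printed | At 338 | At 241 | 241 against printed | Potency implied |
|---|---|---|---|---|---|---|
| -1 | 75 / 75 | 1.0 | 0.94 | 1.03 | +3.2% | 228–328 |
| 1 | 150 / 150 | 1.9 | 1.89 | 2.06 | +8.7% | 295–368 |
| 2 | 300 / 150 | 2.3 | 2.33 | 2.69 | +16.8% | 331–371 |
| 3 | 300 / 300 | 3.8 | 3.77 | 4.13 | +8.7% | 311–347 |
| 4 | 600 / 300 | 4.7 | 4.66 | 5.37 | +14.3% | 322–340 |
| 5 | 600 / 600 | 7.6 | 7.54 | 8.26 | +8.7% | 319–337 |
| 6 | 1,200 / 600 | 9.3 | 9.32 | 10.75 | +15.6% | 335–345 |
| 7 | 1,200 / 1,200 | 15.1 | 15.09 | 16.52 | +9.4% | 332–342 |

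Levels 1 to 7 agree with 338 to within 0.06 million, and none of their implied ranges contains 241. Two rows are imperfect at 338. Level 5 is 7.54 against a printed 7.6, just outside rounding. Level -1 fits 241 and not 338.

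**Step 2: can Table 1 settle it?** At 20 million cells/mL, level 7 would need 11.54/20 = 0.58 mL of HS-110 (printed 0.86). For HS-130 it would need 3.55/20 = 0.18 mL at 338 or 4.98/20 = 0.25 mL at 241 (printed 0.36). Neither potency reproduces the volumes. Working backwards, the level 7 volumes imply 11.54/0.86 = 13.4 million/mL for HS-110. For HS-130 they imply 3.55/0.36 = 9.9 at 338 or 4.98/0.36 = 13.8 at 241. The protocol states no actual lot concentration to compare with these.

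**Step 3: what each combination would mean.** The intended margin is 387.2/150 = 2.58.

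- 338 true and used: only the footnote and the level -1 total need correcting. Doses, ratios and margin stand.
- 241 true and used: ng doses, ratios and margin stand. The Synopsis and the level 1 to 7 totals are wrong.
- Cells set at 241, 338 true: starting OX40L-Ig 150 x 338/241 = 210 ng; margin 387.2/210.4 = 1.84; ratios 1.40:1 and 2.80:1; top dose 1,200 x 338/241 = 1,683 ng.
- Cells set at 338, 241 true: 241/338 = 71% of label; starting dose 107 ng; margin 387.2/107.0 = 3.62; ratios 0.71:1 and 1.43:1; top dose 856 ng.

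**The case against.** The strongest reply is that this is a footnote error with no effect on patients. Two of the four combinations leave the ng doses intact, and a third lowers exposure. The only adverse one needs cells to be set at 241, while the planned totals mostly follow 338. The primary endpoint and the escalation rule rest on counts of events per dose level, and scaling every HS-130 dose by one factor leaves the order of the levels unchanged. Even in the adverse case, the ratios stay within the mouse-tested range of 1.3:1 to 5:1, and Section 2.5 claims a further factor of more than 100 because the dose is not adjusted for weight or body surface area. All of that stands, and it limits the point to a correction with a check. It does not remove the conflict: the footnote that says batch specifications determine the cells is the one that prints 241.

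It is also fair that lot concentrations may be held in batch records or the Investigational Product Manual, which are not available here. Their absence from the protocol is not itself an error. It only means that Table 1 cannot resolve the question.

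Three stronger readings are tempting, and the documents do not support them:

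- A reader might infer that patients were or will be overdosed. Nothing shows which potency sets the administered cells.
- A reader might infer that Table 1 was built on 241, because 13.8 million/mL for HS-130 is then close to 13.4 for HS-110. That assumes both lots had similar working concentrations, which the protocol does not say.
- A reader might take the Section 2.5 statements that the starting dose is under one tenth, and the top dose about 0.8, of the established HS-110 dose as confirming 338. That needs total AD100 cells over a 20 million two-week denominator, which the text does not give. The statements concern HS-110, whose cell number does not depend on HS-130 potency.

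**Conclusion.** The conflict is certain: one lot, two potencies, a factor of 1.40, and Table 2 totals for levels 1 to 7 that contradict the table's own footnote by 9 to 17%. Level -1 goes the other way, so the table as printed is not consistent with either value throughout. Which potency is right, and which one sets the cells, cannot be determined from the documents.

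The 210 ng start and 1.84 margin are an unverified contingency. They require 338 to be the true potency and 241 to be the value used for dosing. In that case the stated margin would fail and the two ratios would no longer sit either side of the 1.3:1 found best in mice. In the reverse case patients would receive 71% of the labelled OX40L-Ig. This should be treated as a document correction with a dosing check, not as a demonstrated dosing error.

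**What to change.** 1. State one verified potency for lot HBI-HS-130-FP-001, identically in the Synopsis and the Table 2 footnote. The sponsor's lot record decides which.
2. Regenerate every Table 2 total, including level -1, as ng divided by potency.
3. Check the Table 1 volumes and the pharmacy or Investigational Product Manual against that potency and the actual lot concentrations.
4. Only if the verified potency is not the one used to set cells, correct the ng labels, the ratios and the NOAEL margin in Section 2.5.

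The cost is an amendment to the text and a check of the manual, with no extra patients, visits or time. If the check shows that cells were set at 241 while 338 is true, the starting-dose margin has to be restated as 1.84.

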2.3.2 Immuno-toxicity Studies

Up until April 2019, over 100 patients with non-small cell lung cancer (NSCLC) have been treated, and over 1000 doses (up to 10 million cells/dose) of the HS-110 cellular vaccine have been administered (IND 14814), without any overt toxicity.

No formal GLP toxicology studies for HS-130 have been proposed or conducted to date. Since HS-130 and HS-110 are species (human)-specific, viable, replication-incompetent whole cell vaccines, that are administered intradermally, experimental experience suggests that safety pharmacology and toxicology studies with HS-130 and HS-110 in animals would be unlikely to predict similar effects in humans due to their nature as xenogeneic cellular entities. The mechanism for hyperacute xenograft rejection of discordant cellular entities (e.g., HS-130 in a mouse model) has been well characterized, involving responses from both innate and adaptive arms of the immune system.^{8,9,10} These responses are rapidly induced and lead to overwhelming pro-inflammatory states that destroy the graft unless the recipient undergoes a conditioning regimen.^{9,13,14} Such conditioning regimens are highly toxic and would modify

the host recipient in ways that would be too confounding for the purposes of studying the safety, pharmacology and toxicology of HS-130.

Based on the results from an *in-vitro* experiment¹⁵ to compare the signaling strength of mouse, monkey and human OX40L-Ig in a human OX40 receptor signaling assay, the potency of OX40L from different species was found to be comparable in its magnitude to activate the human OX40 receptor in the Jurkat/OX40 cell based signaling system. It was observed that monkey (rhesus or cynomolgus) OX40L ligand is similar to human as well as compared to mouse OX40L in the human OX40 receptor assay. This suggests that all three species are compatible and share similar affinity for each receptor allowing for preclinical translation of mouse model results to human.

To study the mechanism of action of cancer vaccines, an intact and syngeneic immune system is required. There are no validated cancer cell line models for *in vivo* experiments in monkeys and the non-human primate tumor models are not validated or well characterized. Therefore, mouse surrogate cell lines in murine animal models were utilized to demonstrate *in vivo* proof-of-concept for activity and to study the toxicokinetics in order to estimate a safe clinical starting dose of HS-130 and HS-110.

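### Table 2's cell totals for dose levels 1 to 7 follow an HS-130 productivity of 338, not the 241 fg/cell in the table's own footnote, for the same lot

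*Combined protocol and SAP*

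**What the plan says.** **HS-130 productivity.** Two values are printed for one lot.

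- Synopsis, test product paragraph: "Lot HBI-HS-130-FP-001: OX40L-Ig concentration = 338 ng" per million cells per 24 hours. For HS-110 it gives "gp96-Ig concentration = 104 ng gp96-Ig/10⁶ cells/24-hr".
- Section 6.1.1, Table 2, asterisk footnote: "For HS-130: Lot HBI-HS-130-FP-001 = 241 fg/cell/24-hr and HS-110: Lot 0000748931 = 104 fg/cell/24-hr".

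The same footnote says how the figure is used: the number of cells needed to reach each ng "dose will be determined based on the specifications for that batch of the drug product".

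**Cell totals.** Table 2 prints totals of 1.0 million AD100 cells at level -1 and 1.9, 2.3, 3.8, 4.7, 7.6, 9.3 and 15.1 million at levels 1 to 7, given every two weeks.

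**Comparison with earlier experience.** The hash footnote says that the total "administered every second week at the highest dose level is similar to or less than the weekly dose of 10 million HS-110 cells" used in the HS-110 study. Section 2.3.2 describes that experience per dose: "over 1000 doses (up to 10 million cells/dose) of the HS-110 cellular vaccine have been administered".

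**The concern.** One fg per cell equals one ng per million cells, so 338 and 241 are rival values of the same quantity. Batch variation cannot explain them, because the lot is the same. The HS-110 figure, 104, agrees in both places. The summary of changes in Appendix III mentions no revision of the productivity.

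HS-130 is the component with no earlier human data (section 2.4), and this figure is its ng-to-cell conversion. An error in it changes both the OX40L-Ig dose delivered and the HS-130 to HS-110 ratio. Two arguments in section 2.5 depend on those quantities: the starting dose lies more than 2.5-fold below the mouse NOAEL, and the 1:1 and 2:1 ratios bracket the mouse findings.

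The totals also support the statement about cell load in the hash footnote, which sets a two-weekly amount against a weekly one without saying that an average is meant.

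**Working it through.** **Totals.** Cells (millions) = HS-130 ng / p + HS-110 ng / 104, where p is the HS-130 productivity. The ng doses are those in Table 2.

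| Level | HS-130 / HS-110 (ng) | Printed | p = 338 | p = 241 | 241 vs printed |
|---|---|---|---|---|---|
| -1 | 75 / 75 | 1.0 | 0.94 | 1.03 | +3.2% |
| 1 | 150 / 150 | 1.9 | 1.89 | 2.06 | +8.7% |
| 2 | 300 / 150 | 2.3 | 2.33 | 2.69 | +16.8% |
| 3 | 300 / 300 | 3.8 | 3.77 | 4.13 | +8.7% |
| 4 | 600 / 300 | 4.7 | 4.66 | 5.37 | +14.3% |
| 5 | 600 / 600 | 7.6 | 7.54 | 8.26 | +8.7% |
| 6 | 1,200 / 600 | 9.3 | 9.32 | 10.75 | +15.6% |
| 7 | 1,200 / 1,200 | 15.1 | 15.09 | 16.52 | +9.4% |

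For example, level 7 is 1,200/338 + 1,200/104 = 3.55 + 11.54 = 15.09, or 1,200/241 + 1,200/104 = 4.98 + 11.54 = 16.52.

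With 338, six of the seven totals match to the printed decimal. Level 5 is 7.54 against 7.6, and 7.6 is twice the printed 3.8 of level 3. With 241 none of levels 1 to 7 matches. Level -1 does not discriminate: 1.0 is the rounded result with 241, but also half of 1.9 after rounding.

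**Effect on dose if the wrong figure is used.**

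- Cells computed with 241, lot secretes 338: 338/241 = 1.40. Level 1 becomes 210 ng instead of 150, and level 7 becomes 1,683 ng instead of 1,200. The ratios become 1.40:1 and 2.80:1.
- Cells computed with 338, lot secretes 241: 241/338 = 0.71. Level 1 becomes 107 ng and level 7 becomes 856 ng. The ratios become 0.71:1 and 1.43:1.

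In the first case the margin to the mHS-130 NOAEL of 387.2 ng (section 2.3.2) falls from 387.2/150 = 2.58 to 387.2/210 = 1.84. Both ratios then lie above the best mouse ratio of 1.3:1 (section 2.3.3).

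**Do the injected volumes settle it?** Dividing the cells needed by the volumes in Table 1 gives the implied million cells per mL:

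| Levels | HS-130, p = 241 | HS-130, p = 338 | HS-110 |
|---|---|---|---|
| -1 | 15.6 | 11.1 | 12.0 |
| 1 | 15.6 | 11.1 | 14.4 |
| 2 | 12.4 | 8.9 | 14.4 |
| 3 | 12.4 | 8.9 | 13.1 |
| 4 to 6 | 13.8 | 9.9 | 13.1 |
| 7 | 13.8 | 9.9 | 13.4 |

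If both products are dosed at a similar usable concentration, the volumes at levels 2 to 7 fit 241 better, although the totals fit 338. The volumes at levels -1 and 1 (0.02 and 0.04 mL of HS-130) are too coarse to help. The only concentration printed is a target of 20 million cells per mL for both products, so this is an inference.

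**Hash footnote.** Level 7 per administration is 15.1/10 = 1.51 times 10 million cells with 338, or 16.5/10 = 1.65 times with 241. Averaged per week it is 0.75 or 0.83 times. The HS-110 part alone is 1,200/104 = 11.54 million, or 1.15 times per administration. Level 6 is 0.93 or 1.07 times, so the lot figure also decides whether level 6 or level 7 is the first to pass 10 million cells per administration.

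**The case against.** The contradiction between the two lot figures cannot be answered from the documents. The case against concerns what follows from it.

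- **The dose effect is conditional.** Patients are dosed by the Table 1 volumes and by batch specifications that are not in the documents. The Table 2 totals are a derived column. If the volumes rest on the correct figure, nobody receives a wrong dose. This stands: 1.40 and 0.71 are consequences of a mismatch, not evidence that one occurred.
- **The totals move less than 1.40-fold.** Most cells are HS-110, so the totals differ from print by 8.7% to 16.8%. This stands too. The 1.40 applies only to the HS-130 conversion.
- **Table 1 is coarse.** The HS-130 volume rises 2.5-fold, from 0.04 to 0.10 mL, for a doubled dose between levels 1 and 2. That limits the precision of any level 1 figure. The pattern at the higher levels still favours 241.
- **The hash footnote is defensible.** It names both intervals, the column is marked as two-weekly, and 15.1 million is printed in the row. No rule uses 10 million cells as a threshold. Rewording it is therefore a clarification, and the main finding does not depend on it.
- **Section 2.5 puts the top HS-110 dose at about 0.8 of the documented dose.** This does not rebut the 1.15. At 104 fg/cell, 10 million cells secrete 1,040 ng, and 1,200/1,040 = 1.15. A ratio of 0.8 would need a reference dose of 1,200/0.8 = 1,500 ng.

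**Conclusion.** The point holds. The protocol gives two productivities for one HS-130 lot, and Table 2's totals for levels 1 to 7 contradict the figure printed beneath them. This rests on plain unit conversion with the printed ng doses and 104 for HS-110, and needs no further assumption.

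The documents do not show which figure is right. It is more than a misprint to be corrected by eye, because the totals and the synopsis point to 338, while the injected volumes point to 241 if the two products have similar usable concentrations. The possible dose error is 1.40 or 0.71 times nominal for the first-in-human component, conditional on cells having been computed with the wrong value.

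The hash footnote is true at level 7 as a weekly average and not per administration. All figures apply to the two lots named.

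**What to change.** 1. Settle one productivity for the HS-130 lot from the batch records, and print it in both the synopsis and the asterisk footnote.
2. Recompute Table 2. If 241 is right, levels -1 to 7 are 1.0, 2.1, 2.7, 4.1, 5.4, 8.3, 10.7 and 16.5 million. If 338 is right, correct the footnote and print 0.9 at level -1 and 7.5 at level 5.
3. State under Table 1 the productivity and cells per mL used for each product, and recompute the HS-130 volumes if they rest on the other figure.
4. As a clarification, say in the hash footnote that level 7 is below 10 million cells per week on average (0.75 or 0.83 times) but above earlier per-dose experience (1.51 or 1.65 times).

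The cost is one lot figure to reconcile, up to eight totals and the HS-130 volumes to check, and one footnote to reword. The stated safety margin becomes less favourable at level 7, and at level 6 too if 241 is right. Nominal ng doses and escalation rules do not change.
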